## **9.4 Data Analysis Plan**

### **9.4.1 Planned Analyses**

#### **9.4.1.1 Patient Disposition and Drug Exposure**

The number of patients who were exposed to the study medication, who completed the study, and who withdrew from the study will be presented, along with reasons for withdrawals.

#### **9.4.1.2 Patient Characteristics**

Patients characteristics including demographics will be summarized with descriptive statistics for continuous variables and with frequency tables for categorical variables. Medical history will be summarized using the Medical Dictionary for Regulatory Activities (MedDRA). Prior and concomitant medications will be summarized using the WHO Drug Dictionary (WHO-DD).

#### **9.4.1.3 Analysis of Safety**

The Clopper-Pearson 95% confidence interval (CI) of the incidence of post-dose levels of ALT or AST that meet the criterion for being considered a safety concern will be calculated for each dosage group. Similarly, the Clopper-Pearson 95% CI of the incidence of GI distress reported by patients during the study will also be calculated. Other AEs will be summarized by using frequency tables. The incidence of abnormal data for safety measures will be presented for each dosage group.

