#### **3.1.1.1 Criteria for Safety Concerns**

As a consequence of liver iron overload and frequent blood transfusions, patients in the target population may have fluctuations of AST and/or ALT that frequently exceed the reference ranges. In recognition of this variability, for each of these enzymes, the criteria for deciding whether an individual patient's increases during the current study is of concern will be set as follows:

- For a patient whose baseline level is within the normal range, the criterion will be reaching a value of 5 times the ULN during the study.
- For a patient whose baseline level is above the ULN, the criterion will be reaching a value of 5 times the baseline value during the study or 10 x ULN.

All cases of patients meeting either of the above criteria at any point during the study must be reported to ApoPharma by the investigator within 24 hours of occurrence, using the sponsor's SAE form.

If at any time during the study a patient's ALT and/or AST values reach a level of **10 x ULN**, do the following:

- If the patient is symptomatic and/or has any other clinically significant abnormal laboratory results, immediately withdraw the patient from the study.
- If the patient is asymptomatic and has no other clinically significant abnormal laboratory results, interrupt treatment and obtain a confirmatory count the next day.
  - If the value is confirmed to be  $\geq 10$  x ULN:
    - Stop treatment, withdraw the patient and complete all end of study assessments scheduled for Day 28
    - Document the event and report it within 24 hours to ApoPharma
    - Monitor the patient daily until the elevated value returns to a level that is regarded as not clinically significant
  - If the confirmatory value is found to be  $< 10$  x ULN, resume treatment as per protocol, and monitor liver enzyme levels within 3 days of resuming therapy.

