## 7 MEASUREMENTS AND EVALUATIONS

### 7.1 Safety Measurements

#### 7.1.1 Medical Events, Adverse Events, and Serious Adverse Events

##### 7.1.1.1 Definition of Medical Events and Adverse Events

*Medical Event (ME):* Any new untoward medical occurrence or worsening of a pre-existing condition in a clinical trial participant that occurs after signing the informed consent form (ICF) but before receiving the first dose of study drug.

*Adverse Event (AE):* Any untoward medical occurrence in a patient who is administered a pharmaceutical or other therapeutic product in a clinical study, not necessarily having a causal relationship with the product. An AE can therefore be any unfavorable and unintended sign, symptom, or disease temporally associated with the use of a product, whether or not considered related to that product.

AEs include:

- Exacerbation of a pre-existing illness, including acute episodes/crisis of a chronic underlying condition
- An increase in frequency or intensity of a pre-existing episodic event or condition
- A condition detected or diagnosed after study treatment administration, even though it may have been present prior to the start of the study
- A continuous persistent disease or symptom present at baseline that worsens following the start of the study
- Accidents (e.g., involving a motor vehicle)
- Reasons for changes in concomitant medication (type of drug and/or dose)
- Medical, nursing, or pharmacy consultation
- Admission to hospital and surgical operations
- Abnormalities in laboratory findings (e.g., clinical chemistry, hematology, urinalysis), ECG, or other assessments (e.g., vital signs) that are not part of a larger medical condition already recorded as an AE and which are judged by the investigator to be clinically significant. The investigator should exercise medical and scientific judgment in deciding whether an abnormal laboratory finding or other abnormal assessment is clinically significant.

AEs do not include:

- A pre-existing disease or condition present or detected at the start of the study that does not worsen
- Hospital admissions or surgical procedures that had been planned prior to enrolment into the study
- The disease or disorder being studied, or a sign or symptom associated with that disease or disorder, unless it has worsened
- An overdose of either the study treatment or concurrent medication without any signs or symptoms

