**Notes:**

- With the exception of hematology, laboratory results obtained at screening will be treated as the baseline values.
- There will be a window of  $\pm 1$  day for assessments done at Days 3 and 7, and of  $\pm 2$  days for assessments done at Days 14, 21, and 28.
- The investigator may increase the frequency of safety evaluations if deemed appropriate for assessment of any clinically significant adverse event. In the case of increases in liver enzymes that meet the criteria for being considered a safety concern, the patient is to be followed until resolution of the event, beyond Day 28 if necessary.
- If a patient withdraws from the study, the End of Study procedures are to be performed at an early termination visit.

Investigators must document their review of each laboratory report by signing or initialing and dating it. Any laboratory values that fall outside a clinically accepted range, or values

that differ significantly from previous values, must be marked by the investigator as either “CS” (clinically significant) or “NCS” (not clinically significant). Any that are marked as CS must be further explained and documented as an AE.

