### **7.1.3 Other Safety Measurements**

#### **7.1.3.1 Physical Examinations**

Physical examination will consist of an examination of head, ears, eyes, nose, throat and neck, respiratory system, cardiovascular system, gastrointestinal system, musculoskeletal system, neurological systems (central and peripheral), and skin, nails, hair, and scalp. A complete examination will be performed at screening, and a symptom-oriented examination will be performed at Day 28. Any abnormalities noted prior to the first dose of study medication will be recorded as either medical history or a medical event (depending on time of occurrence), while any that are noted at the end of the study will be recorded as AEs.

Body weight (without shoes) will be measured at screening only.

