## 9 STATISTICAL ANALYSIS

SAS Windows version 9.3 or higher will be used for statistical analysis. The safety population, defined in [Section 9.3.1](#), will be the primary population for this study.

The continuous and discrete variables for safety data will be summarized with descriptive statistics (mean, median, standard deviation, minimum, and maximum) and frequency tables, respectively, at each assessment.

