### 9.1 Endpoints

#### 9.1.1 Primary Endpoint

The primary endpoint is the incidence of any post-dose occurrence of increases in ALT and/or ALT levels that meet one of the criteria for being considered a safety concern. The safety criteria are:

- For a patient whose baseline level is within the normal range, the criterion will be reaching a value of 5 times the ULN during the study.
- For a patient whose baseline level is above the ULN, the criterion will be reaching a value of 5 times the baseline value during the study or  $>10 \times$  ULN.

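### The planned incidence of abnormal safety data ignores each patient's baseline, so unchanged entry abnormalities are counted with new ones; the examination rule in 7.1.3.1 also conflicts with the AE definition

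*Combined protocol and SAP*

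**What the plan says.** On tabulation, Section 9.4.1.3 (repeated in the synopsis under statistical methods) plans one display for safety measures other than the primary criterion and AEs: "The incidence of abnormal data for safety measures will be presented for each dosage group". Section 9 adds: "The continuous and discrete variables for safety data will be summarized with descriptive statistics", by assessment. No threshold for abnormal, no treatment-emergent definition, no shift table and no change-from-baseline summary is given.

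A baseline does exist. The notes to Section 7.1.2 say: "With the exception of hematology, laboratory results obtained at screening will be treated as the baseline values". Hematology has its own Day 0 sample in Table 5.1. The primary endpoint in Section 9.1.1 uses the baseline: "For a patient whose baseline level is above the ULN, the criterion will be reaching a value of 5 times the baseline value", with 10 x ULN as the alternative. Section 3.1.1.1 gives the reason: "patients in the target population may have fluctuations of AST and/or ALT that frequently exceed the reference ranges".

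On AE recording, Section 7.1.1.1 lists among things that are not AEs: "A pre-existing disease or condition present or detected at the start of the study that does not worsen". Section 7.1.3.1 sends examination findings noted before the first dose to medical history or medical events, and continues: "while any that are noted at the end of the study will be recorded as AEs". For laboratory values, the text after the notes in Section 7.1.2 has the investigator mark each value as clinically significant (CS) or not (NCS), and then: "Any that are marked as CS must be further explained and documented as an AE".

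**The concern.** Every patient is already taking deferiprone IR and is switched to DR with no concurrent control. Section 1.2 asks whether the switch affects liver enzymes, which is a within-patient question, and each patient's own baseline is the only reference available. The protocol accepts this for the primary criterion but does not carry it into the general safety table.

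Patients may enter with out-of-range values. The exclusion criteria reject ALT or AST only above 5 x ULN, so values between 1 and 5 x ULN are admissible. A count of patients with abnormal data then mixes abnormality brought into the study with abnormality that appeared on DR. A reader of the final table could take the first kind for an effect of the new tablet, or could miss a real effect among findings that were already there.

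The examination rule raises a related problem in the AE tables. A site that follows 7.1.3.1 to the letter would report an old, stable finding as an AE; a site that follows 7.1.1.1 would not. The AE counts would then depend partly on which section each site applied.

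**Working it through.** The plan states no figure for this table, so there is none to reproduce. The check is a reading of the text plus an illustration of size.

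**Text, tabulation.**

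1. Section 9.4.1.3 and the synopsis give an incidence per dosage group with no baseline condition.
2. The by-assessment summaries in Section 9 can include screening, so the group's entry level may be visible. They are marginal summaries. If 4 of 15 are abnormal at screening and 4 of 15 at Day 28, they do not show whether these are the same 4 patients.
3. No other part of Section 9 supplies the within-patient link.

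**Text, AE recording.**

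| Type of finding | Section | Condition for becoming an AE |
|---|---|---|
| General rule | 7.1.1.1 | Unchanged pre-existing conditions excluded |
| Laboratory value | 7.1.2 | Marked clinically significant |
| Vital sign | 7.1.3.2 | Clinically significant; refers to 7.1.1.1 |
| Examination finding | 7.1.3.1 | Noted at the end of the study; no other condition |

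Only the last row has neither a significance filter nor a link to baseline or to 7.1.1.1.

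**Illustration of size, for one safety measure.**

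Inputs: n = 15 per group (Section 4.1); p = proportion of patients abnormal at entry on that measure. The protocol does not give p, so 10% to 60% is an assumed range. Assume also that no patient changes from baseline.

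- Expected number counted as abnormal without reference to baseline: 15 x p.
- Probability that at least one is counted: 1 - (1 - p)^15.
- Clopper-Pearson 95% limits for the count, the interval method that Section 9.4.1.3 uses for its other incidences.

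| Assumed p | Expected abnormal of 15 | P(at least one) | 95% CI at that count |
|---|---|---|---|
| 10% | 1.5 | 1 - 0.9^15 = 79% | not a whole number |
| 20% | 3 | 1 - 0.8^15 = 96% | 4.3% to 48.1% |
| 40% | 6 | 1 - 0.6^15 > 99.9% | 16.3% to 67.7% |
| 60% | 9 | 1 - 0.4^15 > 99.9% | 32.3% to 83.7% |

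If only new or worsened values are counted, the result in every row is 0/15, with upper limit 1 - 0.025^(1/15) = 21.8%, so 0 to 21.8%.

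**The case against.** The strongest reply is that 9.4.1.3 is silent on baseline rather than opposed to it, that this is a secondary descriptive display in a study of 30 patients with no power calculation, and that screening summaries will show where the group started. The silence and the secondary role are granted. But a table programmed from the text as written would not use baseline, and group summaries cannot show who changed.

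On 7.1.3.1, one can say that the sentence first sends pre-dose findings to medical history, so the natural reading is that only findings not already recorded become AEs, and that the Day 28 examination is symptom-oriented. That reading may well be intended, but the words do not state it, and the literal text conflicts with 7.1.1.1.

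Three stronger readings are tempting, and the protocol does not support them.

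- *Laboratory AEs are also recorded without regard to baseline.* Under 7.1.2 only values marked clinically significant become AEs, and investigators also review values that differ from earlier ones. Section 3.3 ties the significance of ALT/AST increases to the patient's history. Section 7.1.1.1 also excludes signs of the disease under study unless they have worsened. A stable, known abnormality can be marked not clinically significant.
- *Up to 9 of 15 patients will enter with abnormal ALT, because Section 1.2 cites 60%.* That figure is an upper value for ALT of at least 2 x ULN observed on deferiprone, and Section 1.2 says that in most of these patients the increase returns to baseline. It is not an entry prevalence for this trial. Here 60% serves only as the top of an assumed range.
- *Haemoglobin and ferritin will be abnormal in nearly everyone, so the safety tables can show nothing.* Disease-related tests may well be out of range at entry, but no figure is given. Nothing suggests near-universal abnormality for neutrophils (at least 1.5 x 10^9/L is required at screening), creatinine (above 2 x ULN is excluded), platelets, coagulation or urinalysis.

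**Conclusion.** The point holds for the tabulation and, separately, for the examination rule. As written, the incidence of abnormal data does not separate unchanged entry abnormality from new or worsened abnormality, and no other planned display does so within patients. With no change in any patient, the literal count for one measure would be expected to show 1.5 to 9 of 15 abnormal per group over an assumed entry prevalence of 10% to 60%, where a baseline-referenced count shows 0/15 (95% CI 0 to 21.8%).

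The size rests on that assumed prevalence and on no patient changing. Section 1.2 reports that ALT fluctuates in individual patients, so some will cross the limit by chance and even a baseline-referenced count will not be a pure drug effect. It removes the abnormality that was already there.

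The primary endpoint already refers to baseline and is unaffected. On AEs, the conflict is confined to 7.1.3.1 against 7.1.1.1. The change should be made, because the general safety tables are hard to interpret without it, but the primary result does not depend on it.

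**What to change.** 1. In Section 9.4.1.3 and the synopsis, replace the incidence of abnormal data with the incidence, per dosage group, of abnormality that is new or worsened relative to baseline. Baseline is screening, or Day 0 for hematology. New means in range at baseline and out of range after dosing. The rule for worsening from an abnormal baseline should be fixed before the data are analysed.
2. Add shift tables per group from baseline to the worst post-dose value, so that unchanged, new and worsened findings can be told apart.
3. Reconcile Section 7.1.3.1 with Section 7.1.1.1 by limiting end-of-study examination AEs to findings that are new or worsened since screening.

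The cost is wording in the synopsis and two sections, plus standard tables from data already scheduled for collection. No visit, sample or procedure is added.

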#### **9.4.1.4 Analysis of Acceptability**

For each dosage group, frequency tables will be used to summarize the response to each question of the questionnaire in [Appendix 1](#) on treatment acceptability between Ferriprox IR vs. deferiprone DR. Based on the response to the question on overall preference for one

formulation or the other (Question #4), a one-sample proportion test will be used to test if the overall preference of deferiprone DR is greater than 0.5 for each dosage group.

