## **4 STUDY POPULATION**

### **4.1 Number of Patients**

A total of 30 patients will be enrolled in this study, 15 in each dosing dosage group.

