#### **4.5 Patient Withdrawal**

Patients have the right to withdraw from the study at any time and for any reason without consequence to future care by the investigator or study center.

A patient may be withdrawn from the study at any time, at the discretion of the investigator, for any of the following reasons:

- Medical or safety reasons considered significant by the patient and/or the investigator
- Requirement for concomitant medication that might interfere with the evaluation of study treatment or may be contraindicated
- Receipt of a rescue medication
- Occurrence of other illnesses that might affect the patient's further participation in the study or evaluation of study treatment
- A protocol deviation that might interfere with study assessments, as judged by the investigator
- Repetitive patient non-compliance with the protocol or with instructions of the investigator
- Participation in another clinical trial at any time during the conduct of this study
- Any other situation where, in the opinion of the investigator, continuation of the study would not be in the best interest of the patient

A patient **must** be withdrawn from the study if any of the following conditions apply:

- Pregnant or planning to become pregnant (see [Section 7.1.4](#))
- A confirmed ALT or AST value  $>10 \times \text{ULN}$  (see [Sections 4.5.1.1](#) and [7.1.1.8.1](#))
- A confirmed ANC value  $< 0.5 \times 10^9$  (see [Sections 4.5.1.2](#) and [7.1.1.8.2](#))
- Occurrence of any adverse event characterized as life-threatening or disabling that is not associated with the patient's condition
- Termination of the study by the sponsor

Patients who decide to withdraw participation in the study should always be contacted, if possible, in order to ask about the reason for withdrawal, whether any adverse events (AEs) occurred, and use of concomitant medications. A withdrawn patient should return for an early termination visit and a follow-up visit. All investigational product and materials should be returned. If any AEs occurred, the investigator must attempt to follow up the outcome until resolution.

If a patient withdraws or is withdrawn before completing the study, the date and reason for the withdrawal must be entered on the source document and on the appropriate page of the electronic case report form (eCRF), and all other appropriate eCRF pages must be completed.

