**Table 5.1 Table of study procedures**

Study Procedure	Screening Day -14 to -1	Baseline Day 0	Day 3 (±1 day)	Day 7 (±1 day)	Day 14 (±2 days)	Day 21 (±2 days)	Day 28 (±2 days) or early termination 
Informed consent	X						
Demography	X						
Medical history 	X						
Medication history	X	X					
Eligibility criteria	X	V					
Biochemistry 	X		X	X	X	X	X
Hematology 	X	X		X	X	X	X
Coagulation 	X						X
Serology 	X						
Urinalysis 	X						X
Physical examination 	X						X
Vital signs	X						X
Serum pregnancy test 	X						X
Dispense study medication		X					
Dosing	Twice-daily from Day 1 to Day 28						
Collect study medication containers							X
Treatment compliance							X
Medical events	X	X					
Adverse events/ serious adverse events	Throughout the study						
Concomitant medications	Throughout the study						
Acceptability questionnaire							X

V: Verify

1. If deemed necessary, patients with ongoing adverse events may be asked after the last dose to provide further blood samples until resolution
2. Medical history is to include a record of at least 10 measured ALT and AST levels
3. Biochemistry: Total protein, gamma-glutamyl transferase (GGT), lactate dehydrogenase (LDH), sodium, potassium, chloride, glucose, bilirubin (total, direct, and indirect), alanine aminotransferase (ALT), aspartate aminotransferase (AST), albumin, blood urea nitrogen, calcium, creatinine, uric acid, alkaline phosphatase, amylase, serum ferritin, and blood iron
4. Hematology: Hemoglobin, total WBC count, ANC, MCV, and platelet count
5. Coagulation: Prothrombin Time (PT), Partial Thromboplastin Time (PTT), and International Normalized Ratio (INR)
6. Serology: HIV Ag/Ab Combo, hepatitis B (HBsAg (B)), and hepatitis C (anti-HCV (C))
7. Urinalysis: Color, appearance, specific gravity, pH, leukocyte, protein, glucose, ketones, bilirubin, blood, nitrite, urobilinogen. Microscopic examination must be performed if dipstick test is outside the reference range for leukocyte, blood, nitrite or protein. (Note: for patients with sickle cell disease, samples are to be sent for microscopy if there is blood in the urine or three or more “plus signs” for protein.)

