#### 9.1.2 Secondary Endpoints

Secondary endpoints are as follows:

- The assessment of tolerability will be based on the incidence of gastrointestinal (GI) distress reported by patients during the study.
- The assessment of acceptability will be based on the number of patients who indicate that they prefer the DR formulation over Ferriprox IR after considering their preference with respect to scheduling, ease of administration, and tolerability.

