### APPENDIX 1: QUESTIONNAIRE ON TREATMENT ACCEPTABILITY

Patient Number: \_\_\_\_\_

Site Number: \_\_\_\_\_

Date: \_\_\_\_\_

1. What is your preference between deferiprone delayed release (DR) tablets and Ferriprox tablets with respect to the dosing schedule (twice a day vs. three times a day)?

				
Much prefer deferiprone DR	Somewhat prefer deferiprone DR	No preference	Somewhat prefer Ferriprox	Much prefer Ferriprox

2. What is your preference between deferiprone DR and Ferriprox with respect to taking the tablets (ease of swallowing, feel of tablet, aftertaste, or any other factors)?

				
Much prefer deferiprone DR	Somewhat prefer deferiprone DR	No preference	Somewhat prefer Ferriprox	Much prefer Ferriprox

3. What is your preference between deferiprone DR and Ferriprox with respect to any side effects (upset stomach, joint pain, or any other problems)?

				
Much prefer deferiprone DR	Somewhat prefer deferiprone DR	No preference	Somewhat prefer Ferriprox	Much prefer Ferriprox

4. After considering the above factors, if you had the choice of which formulation to take in future, which one would you prefer?

	
Deferiprone DR	Ferriprox

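### Patients who stop DR and do not return are never asked Question 4, and 9.4.1.4 sets no denominator or missing-answer rule, so a test on answers alone would probably overstate preference for DR

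*Combined protocol and SAP*

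**What the plan says.** **Endpoint.** Section 9.1.2 states: "The assessment of acceptability will be based on the number of patients who indicate that they prefer the DR formulation over Ferriprox IR". It names a count of patients and no denominator.

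**Test.** Section 9.4.1.4 works from Question 4 alone: "Based on the response to the question on overall preference". On that basis, "a one-sample proportion test will be used to test if the overall preference of deferiprone DR is greater than 0.5 for each dosage group". The synopsis says the same. Neither place says who is in the denominator or how a patient without an answer is counted.

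**Question.** Question 4 in Appendix 1 asks "if you had the choice of which formulation to take in future, which one would you prefer" and offers two boxes, DR or Ferriprox. There is no neutral option.

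**When it is asked.** In Table 5.1 the row "Acceptability questionnaire" is marked in one column only, Day 28 or early termination. Section 5.1 requires that visit to take place at the study site. Section 3.1 says that patients who withdraw are requested to return for it.

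**Contact with patients who withdraw.** Section 4.5 says that they should be contacted, if possible, "in order to ask about the reason for withdrawal, whether any adverse events (AEs) occurred, and use of concomitant medications". Preference is not on the list.

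**Numbers.** Section 4.1: "A total of 30 patients will be enrolled in this study, 15 in each dosing dosage group". Under 4.5.3, withdrawn patients are not replaced.

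**The concern.** A patient who finds DR hard to tolerate, goes back to Ferriprox and skips the site visit is plausibly the patient least likely to choose DR. The plan has no means of recording that patient's view, although it does provide for a contact at which the question could be put. If the test then uses only the answers received, the missing answers come mostly from one side, and the proportion compared with 0.5 moves towards DR.

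The sponsor has reason to take this route seriously. Section 1.1 reports more nausea and vomiting on DR than on Ferriprox in study LA58-0117, with GI events leading to voluntary withdrawal in 2 cases, and section 1.2 says that GI events will be watched here for that reason. Acceptability is one of the two secondary objectives, and this is the only hypothesis test that section 9 describes. With 15 patients per group, one or two missing answers can decide it. Leaving the denominator open also means that it could be chosen after open-label results are known.

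**Working it through.** The plan gives no power, significance level or dropout rate for this test, so there is no stated figure to reproduce. The check has two parts: who can supply an answer, and how far a few missing answers could move the result.

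**1. Who supplies an answer**

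| Patient | Asked Question 4? | Source |
|---|---|---|
| Completes treatment | Yes, at Day 28 | Table 5.1, 5.1 |
| Withdraws and attends early termination | Yes | 3.1, Table 5.1, 5.1 |
| Withdraws, reached by contact only | No | 4.5 |
| Withdraws, not reached | No | 4.5 |

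The gap is confined to the last two rows. The third can be closed at almost no cost.

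**2. Effect on one group**

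Inputs:
- n = 15 per group (4.1), no replacement (4.5.3), null value 0.5, direction greater (9.4.1.4).
- Assumptions, none of them in the plan: 2 of the 15 give no answer and would not choose DR; one-sided level 0.05; exact binomial test.

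Formula: p = sum over j from x to m of C(m, j) / 2^m, where x is the number choosing DR. The denominator m is 13 if the two are excluded and 15 if they are counted as not preferring DR.

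Worked case, x = 10:
- m = 13: (286 + 78 + 13 + 1)/8192 = 378/8192 = 0.046
- m = 15: (3003 + 1365 + 455 + 105 + 15 + 1)/32768 = 4944/32768 = 0.151

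| x | x/13, exact p | x/15, exact p | Conclusion at one-sided 0.05 |
|---|---|---|---|
| 9 | 69.2%, 0.133 | 60.0%, 0.304 | Same (not significant) |
| 10 | 76.9%, 0.046 | 66.7%, 0.151 | Changes |
| 11 | 84.6%, 0.011 | 73.3%, 0.059 | Changes |
| 12 | 92.3%, 0.002 | 80.0%, 0.018 | Same (significant) |

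A single lost patient can be enough: 11/14 gives p = 0.029, against 0.059 for 11/15.

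**3. Does the form of the test matter?**

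The plan does not say whether the test is exact. With the uncorrected normal test, z = (x/m − 0.5)/√(0.25/m):
- x = 10: p = 0.026 for 10/13 and 0.098 for 10/15. The conclusion still changes.
- x = 11: p = 0.006 for 11/13. For 11/15, z = 0.2333/0.1291 = 1.81 and p = 0.035. The conclusion does not change.

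So the change at 10 appears under both tests, and the change at 11 only under the exact test.

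**4. Average effect if true preference is 0.5**

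Let each patient who would not choose DR be missing with probability q (assumed), and exclude the missing. The expected share among answers is close to 0.5/(1 − 0.5q); for q = 0.2 this is 0.5/0.9 = 0.556. The false-positive rate is the sum, over all combinations of x and the number missing, of the probabilities of those where the test rejects at one-sided 0.05.

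| q | Mean estimate | False-positive rate, exact | False-positive rate, normal |
|---|---|---|---|
| 0 | 0.500 | 0.018 | 0.059 |
| 0.1 | 0.526 | 0.040 | 0.069 |
| 0.2 | 0.556 | 0.069 | 0.100 |
| 0.3 | 0.588 | 0.104 | 0.149 |
| 0.4 | 0.625 | 0.147 | 0.219 |

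**The case against.** **The denominator is open, not fixed at responders.** A reader might infer that the test as written excludes non-responders and that preference for DR is therefore overstated. The documents do not go that far. Section 9.4.1.4 names no denominator, sections 9 and 9.3.1 make the safety population primary for the study, and 9.1.2 speaks of a number of patients. An all-dosed denominator is a permitted reading, and if missing answers then counted as not preferring DR, the upward bias would not arise. What stands is that neither the denominator nor the missing-answer rule is written down.

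**Most withdrawals are covered.** The early termination visit includes the questionnaire. Patients are told at baseline to attend it within one month of the last dose (5.1), and 4.5 says that they should return. Reasons for withdrawal (9.4.1.1) and the GI distress interval (9.4.1.3) would also show intolerance among those lost. This narrows the problem to non-attenders but does not supply their answer to Question 4.

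**The earlier study gives no rate.** A reader might take the 2 withdrawals in LA58-0117 as support for losing 2 of 15. They do not provide it. Those subjects were healthy volunteers dosed fasting at 100 mg/kg/day for 3 days. Section 1.1 does not give the arm of the two, and leaving treatment is not the same as leaving a questionnaire blank. Patients here take DR with food, at about the daily dosage they already take as Ferriprox. The earlier study shows a possible mechanism only.

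**Counting every missing answer against DR can err the other way.** Section 4.5 lists exits such as pregnancy, other illness or termination by the sponsor, and 4.7 adds a needed change in chelation. Such patients may have liked DR. This objection stands, and it is why that rule belongs in a sensitivity analysis and not in the main one.

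**Conclusion.** The point holds as a minor one. Withdrawing patients who do not attend the site visit cannot contribute to Question 4, and the plan does not say how their absence is treated. If they are excluded, and if some left because of intolerance, the estimate is likely to favour DR. Neither condition is certain, so an overstatement is likely under them but not established. Losses unrelated to DR need not push the result in that direction.

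The size cannot be fixed from the documents. With 2 of 15 lost, an assumption, the conclusion at one-sided 0.05 changes at 10 DR answers under either form of the test, at 11 only under the exact test, and not at 9 or 12. The level and the form of the test are also assumptions.

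This concerns a secondary endpoint in an unpowered, open-label study of 30 patients. It does not touch the primary endpoint or the enrolment rules.

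**What to change.** 1. **Section 4.5:** add Question 4 to the contact with any withdrawing patient who does not attend the early termination visit.
2. **Section 9.4.1.4 and the synopsis:** say which denominator the main test uses, report the number of missing Question 4 answers in each dosage group, and add a sensitivity analysis over all dosed patients. Possible wording: *The number of patients without an answer to Question 4 will be given for each group. As a sensitivity analysis, the proportion and test will be repeated with every patient who took at least one dose of DR in the denominator, a missing answer being counted as not preferring DR.*

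The cost is one extra question by telephone, on a contact that is already planned, and a few lines of text. Treatment and visits do not change. The sensitivity figure may be slightly less favourable to DR, partly through patients lost for unrelated reasons; the count of missing answers, read beside the reasons for withdrawal, lets the reader judge that.
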